Two different patches will be dispensed to subjects in the abaloparatide-sMTS group. The ultra-low bioburden patches will be dispensed from Day 1 to all subjects. Sterile patches (the patches intended for commercial use) will be dispensed to subjects after confirmation that the sterile product is bioequivalent to the ultra-low bioburden product (Study 058-05-023). For the abaloparatide-sMTS group, the duration of study drug exposure, duration category in months, number of doses delivered and percent compliance with study drug administration using two calculations of percent compliance will also be summarized by patch type (ultra-low bioburden, sterile) for the Safety, mITT and PP populations.

If a subject is shown to be  $<80\%$  compliant with study drug administration using both calculations of study drug administration compliance for abaloparatide-sMTS group, or is  $<80\%$  compliant with study drug administration using both calculations of study drug administration compliance for the abaloparatide-SC group, this subject will be considered as having a critical protocol deviation and thus excluded from the PP Population.

Subjects' drug exposure and compliance will be carefully reviewed against the onset of the COVID-19 pandemic. Each subject's study drug exposure and compliance prior to 01 March 2020 and on or after 01 March 2020 will be calculated based on information collected from the subject diary:

- For subjects with last dose date prior to 01 March 2020 and subjects with first dose date on or after 01 March 2020, their duration of study drug exposure (days), number of doses delivered, and percent compliance to study drug administration relative to 01 March 2020 will be calculated as above based on the missed doses in subject diary
- For subjects who started taking the study drug prior to 01 March 2020 and continued on or after 01 March 2020, their duration of study drug exposure and compliance before 01 March 2020 and on or after 01 March 2020 will be calculated as follow:
  - Durations of study drug exposure relative to 01 March 2020:
    - Duration before 01 March 2020 = 29 February 2020 – date of first dose + 1
    - Duration on or after 01 March 2020 = Overall duration of study drug exposure – duration before 01 March 2020; where overall duration of study drug exposure = last dose date – first dose date + 1

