The study drug exposure and percent compliance to study drug administration before 01 March 2020 and on or after 01 March 2020 will be summarized by treatment group for the Safety, mITT and PP populations. Similar summaries will not be provided by patch type (ultra-low bioburden, sterile) since the switch from ultra-low bioburden patch to sterile patch for subjects in abaloparatide- sMTS group did not occur until after 01 March 2020.

The number (%) of subjects with any missed dose or dose interruption as recorded on the Dose Interruption Log eCRF will be summarized by treatment group, along with the reason(s) for missed/interrupted dose(s) for the mITT, PP, and Safety populations. If a subject reported a start date for the missed/interrupted dose but no corresponding start date for the resumption of study drug, the occurrence of the missed dose/dose interruption will not be included in the summary. The total number of days with missed/interrupted dose for each subject will be calculated and summarized by descriptive statistics and in the following categories: 1-7 days, 8-14 days, 15-28 days, >28 days by treatment group.

Study drug exposure and study drug administration compliance data will be listed by treatment (including patch type for abaloparatide-sMTS group), study site, and subject number.

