#### **4.3.2. Abaloparatide-sMTS Patch Adhesion Scores**

Patch adhesion will be assessed daily by subjects randomized to the abaloparatide-sMTS treatment group using the following scoring system:

- 0 =  $\geq 90\%$  adhered (essentially no lift off the skin)
- 1 =  $\geq 75\%$  to  $< 90\%$  adhered (some edges only lifting off the skin)
- 2 =  $\geq 50\%$  to  $< 75\%$  adhered (less than half of the patch lifting off the skin)
- 3 =  $> 0\%$  to  $< 50\%$  adhered but not detached (more than half of the patch lifting off skin without falling off)
- 4 = 0% adhered – patch detached (patch completely off the skin)

A summary table using descriptive statistics will be provided combining all patch adhesion scores collected in the study. Frequency counts (and percentages) of all patch adhesion scores will be presented. The summaries will also be presented by patch type (ultra-low bioburden, sterile).

The mean of the patch adhesion scores collected from Day 1 to Month 12/EOT will be calculated for each subject and summarized using descriptive statistics. Each subject's best adhesion score and worst adhesion score will also be summarized. In addition, frequency counts (and percentages) for each subject's best adhesion score and for each subject's worst adhesion score from Day 1 to Month 12/EOT will be provided. For subjects treated with both patch types (ultra-low bioburden, sterile), the mean patch adhesion scores will also be calculated for each patch type for each subject for the respective period of treatment of the patch type. Each subject's best adhesion score and worst adhesion score by patch type will also be summarized for the respective period of treatment of the patch type. Frequency counts (and percentages) for each subject's best adhesion score and for each subject's worst adhesion score by patch type will be presented for the respective period of treatment of the patch type.

The percentage of patches that are  $\geq 75\%$  adhered (adhesion score  $\leq 1$ ) will be summarized by patch type and overall for abaloparatide-sMTS treatment group. Statistical assessment of patch adhesion will be evaluated via the following hypothesis test:

- $H_0: p \leq 80\%$  versus  $H_1: p > 80\%$
- $H_0$  is rejected if the 95% lower confidence limit for  $p$  is greater than 80%

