where  $p$  is the estimated percentage of patches that are  $\geq 75\%$  adhered. Two-sided 95% CIs for  $p$  will be provided for each patch type and overall using a model-based method as primary analysis and using Wilson's Score method as sensitivity analysis. Considering that for each subject, the patch adhesion score is collected daily using the subject diary during the treatment period, the model-based method will use a GEE (Generalized Estimating Equation) model assuming binomial distribution and including treatment group as fixed categorical effect with an unstructured correlation matrix to model the within-subject errors. For patch type comparison, the model will include patch type as fixed categorical effect. The p-value will be reported for patch type difference (ultra-low bioburden vs sterile).

All analyses described in this section will be presented for the Safety, mITT and PP populations. The analysis will not be provided for the ITT population since untreated subjects in the ITT population will not have exposure data.

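### The patch-type p-value for adhesion has no adjustment for time on treatment, although sterile patches always come after ultra-low bioburden patches

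*SAP*

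**What the plan says.** SAP 4.3.2 counts a patch as a success if it is at least 75% adhered (score 0 or 1). On who scores, it says: "Patch adhesion will be assessed daily by subjects randomized to the abaloparatide-sMTS treatment group". The success percentage is compared with 80% through a confidence limit, for each patch type and overall. The main method is a binomial GEE, "including treatment group as fixed categorical effect with an unstructured correlation matrix to model the within-subject errors". For the comparison of the two patches the SAP adds: "For patch type comparison, the model will include patch type as fixed categorical effect". It then reports a p-value for that difference. No day, month, visit or calendar period is named in the model.

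The order of the patches is set out in SAP 4.3.1: "The ultra-low bioburden patches will be dispensed from Day 1 to all subjects". Sterile patches, the version meant for the market, "will be dispensed to subjects after confirmation that the sterile product is bioequivalent to the ultra-low bioburden product" in a separate study. The same section records that "the switch from ultra-low bioburden patch to sterile patch for subjects in abaloparatide- sMTS group did not occur until after 01 March 2020".

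SAP section 5 lists the adhesion analysis among the additions to the protocol-specified analyses.

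**The concern.** Patch type is neither randomised nor counterbalanced. In a subject who uses both patches, the planned order puts every sterile day after every ultra-low bioburden day. Any change in adhesion with time on treatment therefore enters the patch-type coefficient.

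Such a change is plausible from the design, though the documents do not show one. Subjects are trained and self-administer for the first time on Day 1 (Protocol 5.6). They score adhesion themselves every day of the Treatment Period (Protocol 6.6.5), in an open-label study. Learning to apply the patch, skin changes or drift in self-scoring could each move the rate. Subjects who leave before the switch contribute only ultra-low bioburden days, which adds a selection effect.

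At stake is the SAP's only between-patch adhesion test for the commercial product. A rising trend would flatter the sterile patch or cover a real loss of adhesion; a falling trend would count against it wrongly.

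**Working it through.** **1. The plan's own figure.** The documents give no power, sample size or error rate for this test beyond the general two-sided 5% level (SAP 3.2). The one planned number used here is 237 sMTS subjects (SAP 3.1). It is consistent with the plan: 426 / 0.90 = 473.3, rounded up to 474, which is 2 × 237.

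**2. What the model can adjust for.** Only sMTS subjects score adhesion, so the treatment-group effect is constant in these data. The correlation matrix describes dependence and leaves the mean model without a time term. The patch coefficient is thus the patch effect plus the trend multiplied by the gap in treatment time between the two patch types.

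**3. The bias by hand.** Assume no patch difference and log-odds that drift linearly from month 1 to month 12 (11 steps) by ln(OR).

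- *Within subject.* For a first sterile month s, the ultra-low bioburden months 1 to s−1 average s/2 and the sterile months s to 12 average (s+12)/2. The gap is 6 months for any s, so the bias is (6/11) × ln(OR): 0.122 for OR 1.25 and 0.221 for OR 1.5. Exchangeable GEE fits gave 0.108 and 0.200; population-averaged log odds ratios are somewhat smaller.
- *Pooled over subjects.* Assume s is uniform on 2 to 12, 30% never switch and nobody drops out. Switchers then average 6 ultra-low bioburden months (month-sum 26) and 6 sterile months (month-sum 52, mean 8.67). The ultra-low bioburden mean month is (0.7×26 + 0.3×78) / (0.7×6 + 0.3×12) = 41.6 / 7.8 = 5.33. The gap is 3.33 months and the bias (3.33/11) × ln(OR): 0.068 and 0.123. Independence fits, which included 10% dropout, gave 0.066 and 0.120.

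**4. Rejection rates with equally adhering patches.** Assumptions not in the documents: 95% success in month 1 for the median subject; subject SD 1.0 or 1.5 on the logit scale; 30% or 60% never switching; s uniform on 2 to 12. Each simulation has 237 subjects with 30 patches a month for 12 months. Independence: 1,000 runs per setting, 10% dropout. Exchangeable: 200 runs (150 with month), SD 1.0, 30% never switching, no dropout. Ranges run over the SD and never-switching settings.

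| Trend OR, month 12 vs 1 | Independence, patch only | Exchangeable, patch only | Independence, plus month | Exchangeable, plus month |
|---|---|---|---|---|
| 1.0 | 5.3–6.8% | 4.0% | 5.5–6.6% | 4.7% |
| 1.25 | 7.4–10.5% | 83% | 5.2–7.1% | 2.7% |
| 1.5 | 10.1–22.7% | 100% | 5.5–6.9% | 4.7% |
| 2.0 | 15.2–49.8% | not run | 5.1–7.1% | not run |
| 0.67 | 7.9–22.7% | not run | 5.2–6.7% | not run |

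**5. A second set of assumptions.** Mean adhesion starts near 85%, subject SD is 1.2, switches fall in months 4 to 12, 25% never switch and 15% drop out (300 runs independence, 80 exchangeable). For linear drifts of 0, +1, +2 and +4 points, the patch-only test rejects 4.0%, 6.3%, 12% and 29% (independence) and 3.8%, 44%, 84% and 100% (exchangeable). A 2-point fall gives 15% and 91%. With month added, the rates for the four upward-drift settings are 4.3%, 5.3%, 5.3% and 8.0% (independence) and 10%, 10%, 3.8% and 6.2% (exchangeable, Monte Carlo SE about 2.5 points).

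**6. Masking.** With a true patch OR of 0.7 and a trend OR of 2.0 (independence, 500 runs), the difference is detected 24% of the time unadjusted and 73% with month in the model.

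**7. Why two stand-in correlation structures.** An unstructured matrix over 360 daily scores has 360 × 359 / 2 = 64,620 correlations against about 237 subjects. It was not fitted here.

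**The case against.** The strongest reply concerns consequence. The comparison sits under exposure to study drug, outside the efficacy and safety sections. No margin, claim or decision rule attaches to the patch-type p-value. The switch to sterile patches depended on a separate bioequivalence study. The adhesion hypothesis that has a rule is the 80% criterion, assessed for each patch type separately. All of this stands.

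A reader might infer that the sterile patch could fail its adhesion criterion because of the missing term. The documents do not support that: the criterion uses each patch type's own confidence limit, not the between-patch p-value. Even in the assumed fall from 85% to 83%, with 120 to 178 subjects (also assumed) contributing sterile data, the expected lower limit for sterile is about 80.1 to 81.7%.

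The size is also open to challenge. Adhesion level, drift, switch timing and dropout are all assumed, and the same 2-point drift gives 12% or 84% depending on the working correlation. This stands too: no single inflated error rate can be attributed to the SAP.

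Finally, the evidence for the remedy is not uniform. In the second set of simulations the month-adjusted test rejected 10% in two exchangeable settings (80 runs) and 8.0% in one independence setting (300 runs). The larger runs in the table, at 2.7 to 7.1%, are better support, but they too assume that switches are spread over treatment months.

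**Conclusion.** The point holds in a limited form. As specified, the patch-type test mixes a product effect with a time-on-treatment effect. It can reject when the patches adhere equally, or miss a real difference, if adhesion changes over the year. Without such a change it is close to nominal, at about 4 to 7%. With modest drift, illustrative rejection is about 7 to 30% under independence and much higher under an exchangeable structure.

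Two stronger readings are tempting and should be resisted. The first is that the test simply compares early with late treatment. The confounding is partial: a calendar trigger should spread switches over different treatment months, and SAP 4.3.2 treats subjects who used both patch types as a subset. The second is that 84 to 100% is the SAP's error rate. Those figures need an assumed drift and a correlation structure that the SAP does not specify.

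The effect is confined to a supportive device comparison. The 80% criterion and the BMD non-inferiority conclusion are unaffected. A change is still worthwhile because it is cheap and this is the only between-patch adhesion test.

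**What to change.** In SAP 4.3.2, add treatment month (time since first patch, categorical or smooth) as a fixed effect alongside patch type in the patch-type GEE. Take the difference, its interval and the p-value from that model.

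First tabulate patch type by treatment month to confirm that both types occur in the same months. Overlap is expected because the switch follows a calendar event, but the documents give neither the switch date nor enrolment dates.

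State that calendar-time effects remain after this adjustment, and label the p-value exploratory.

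The cost is one model term, one table and a sentence or two of text, with no new data. The interval for the patch-type difference will be somewhat wider, because mainly the treatment months containing both patch types inform it.

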#### **4.3.3. Patch Wear Time**

Patch wear time will be summarized for subjects randomized to abaloparatide-sMTS. Although the subject diary includes a field for “Time patch was removed/detached”, the information from this field was recorded on the database as time of “5 Minutes Post-dose Evaluation”. The patch wear time will be calculated as the difference between ‘Time Patch Applied to Thigh’ (as recorded on the subject diary and the database) and time of ‘5 Minutes Post-dose Evaluation’.

For each patch, the subject diary allows for only one date to be recorded. This results in calculated patch wear times that are negative (< 0 minutes) for patches applied before midnight but removed at or after midnight. To ensure appropriate calculation of patch wear time in such circumstances, 24 hours will be added to the patch removal time so that the patch wear time will be re-calculated using the updated patch removal time for records that meet all of the following conditions:

1. Patch application time is after 12:00 pm; and
2. Patch removal time is before 9:00 am; and
3. Original calculated patch wear time  $\leq -12 \times 60$  minutes

where original calculated patch wear time = patch removal time minus patch application time, as recorded on the subject diary.

Negative patch wear times that cannot be corrected by the algorithm above will be excluded from the analysis.

Patch wear time collected at each study visit will be summarized using descriptive statistics by visit. Patch wear time collected over the entire treatment period will also be summarized using descriptive statistics. In addition, the longest wear time and shortest wear time for each subject over the entire treatment period will be summarized.

Patch wear time will also be summarized using the following categories:

- < 4 minutes
- $\geq 4$  minutes – 6 minutes
- $> 6$  minutes – 7 minutes
- $> 7$  minutes

The number (%) of subjects with patch wear time in each of the above categories at each study visit will be presented. The number (%) of patches belonging to each of the above categories over the entire treatment period will also be presented. In addition, similar categorical summaries will be provided for the longest wear time and the shortest wear time for each subject over the entire treatment period.

All analyses described in this section will be performed for both patch types (ultra-low bioburden, sterile) and overall using the Safety population.

#### **4.3.4. Nutritional Supplements Exposure**

Subject exposure to Vitamin D and calcium supplements will be tabulated separately in terms of total amount of IU (for Vitamin D) and mg (for calcium) received (equal to total dispensed minus total returned) and duration of exposure (Duration of Supplement Exposure (days) = date of last dose – date of first dose + 1) by treatment group using the Safety population.

Summary statistics for the average Vitamin D supplement exposure per day (= ([total dispensed minus total returned] / duration of exposure)) will also be presented separately by treatment group. Similarly, summary statistics will be provided for the average calcium supplement exposure per day.

#### **4.3.5. Concomitant Medication**

Concomitant medications will be coded using WHO-DD. The number (and percentage) of subjects taking medications will be tabulated by Anatomical Therapeutic Chemical (ATC) class, PT, and treatment group for the Safety population.

The tabulations will include concomitant medications taken from the date of the first dose of study drug (Day 1) until 30 days after the last dose of study drug. Medications that did not end prior to the first dose of study drug will be included in the summary.

Prior medications (those with start date prior to the first dose of study drug) will also be summarized by ATC, PT, and treatment group.

If both start date and stop date are missing, the medication will be assumed to occur both prior and concomitantly.

All recorded concomitant medications will be presented in a by-subject listing.

To explore the effect of the COVID-19 pandemic, summaries for the prior medications and concomitant medications will also be presented for the following:

- By region (North America and Europe).
- By medication start dates (medications start before 01 March 2020, vs medications start on or after 01 March 2020). For the calculation of percentages, the denominator includes all subjects in the safety population for the relevant treatment group.

#### **4.3.6. Concomitant Procedures**

All surgical, therapeutic, or diagnostic procedures performed during the study as a result of an (other) action taken due to an AE were captured on the Concomitant Procedures Log eCRF.

These procedures will be coded using MedDRA Version 24.0. The number (and percentage) of subjects that had procedures will be tabulated by procedure class, PT, and treatment group for the Safety population.

The tabulations will include concomitant procedures, defined as those procedures with a start date on or after the date of the first dose of study drug (Day 1) until 30 days after the last dose of study drug. Procedures that did not end prior to the first dose of study drug will be included in the summary.

Prior procedures (those with start date prior to the first dose of study drug) will be summarized separately by procedure class, PT, and treatment group.

If both start date and stop date are missing, the procedures will be assumed to occur both prior and concomitantly.

All recorded concomitant procedures will be presented in a by-subject listing.

To explore the effect of the COVID-19 pandemic, summaries for the prior procedures and the concomitant procedures will also be presented for the following:

- By region (North America and Europe).
- By procedure start dates (procedures with start date before 01 March 2020, vs procedures with start date on or after 01 March 2020). For the calculation of percentages, the denominator includes all subjects in the safety population for the relevant treatment group.

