- TEAEs by SOC, PT and relationship to the study drug (related or not related)
- TEAEs by PT

*Note: which will be sorted in descending order of total number of subjects with the preferred term in the overall column.*

- Treatment-related TEAEs by SOC and PT
- Most Common ( $\geq 5\%$  in either treatment group) TEAEs by SOC and PT
- Severe TEAEs by SOC and PT
- Treatment-related Severe TEAEs by SOC and PT
- Serious TEAEs by SOC and PT
- Treatment-related Serious TEAEs by SOC and PT
- TEAEs leading to study drug withdrawal by SOC and PT
- TEAEs leading to discontinuation from study by SOC and PT
- TEAEs leading to death by SOC and PT
- TEAEs leading to study drug interruption by SOC and PT
- Non-TEAEs by SOC and PT.

SOCs will be sorted in alphabetical order. Within an SOC, AEs will be sorted in descending order of the total number of subjects with the PT in the overall group.

To explore the relationship between TEAEs and the duration of study drug exposure, the incidence of TEAEs by time of onset will be presented for the following categories:  $\leq 1$  month,  $> 1$  to  $\leq 3$  months,  $> 3$  to  $\leq 6$  months,  $> 6$  to  $\leq 9$  months, and  $> 9$  months, by treatment group, SOC, and PT. Subjects with multiple occurrences of an AE within a time period will be counted once in each time period that an onset of the AE occurs.

To evaluate the relationship between TEAEs and antibody status, the incidence of TEAEs will also be summarized by antibody status (ADA-, ADA+/Nab+, ADA+/Nab-, All ADA+, and Overall), SOC, and PT using the Antibody population. A summary of TEAEs by PT and antibody status will also be presented by treatment group, in which TEAEs will be sorted in descending order of total number of subjects with the preferred term.

To explore the effect of the COVID-19 pandemic on reported AEs, summaries of TEAEs by SOC and PT, TEAEs leading to treatment discontinuation, and serious TEAEs will also be presented:

- by AE onset date (AE occurs before 01 March 2020, vs AE occurs on or after 01 March 2020)
- by region (North America and Europe)

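### The SAP summaries of medications, procedures and TEAEs split at 01 March 2020 ignore time at risk, so before and after percentages are not comparable and cannot isolate a pandemic effect

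*SAP*

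**What the plan says.** SAP 4.3.6 gives the purpose: "To explore the effect of the COVID-19 pandemic, summaries for the prior procedures and the concomitant procedures will also be presented". One of the two presentations is by calendar date: "procedures with start date before 01 March 2020, vs procedures with start date on or after 01 March 2020". The denominator for that split follows: "For the calculation of percentages, the denominator includes all subjects in the safety population for the relevant treatment group". SAP 4.3.5 does the same for medications ("medications start before 01 March 2020, vs medications start on or after 01 March 2020") with the same rule: "the denominator includes all subjects in the safety population for the relevant treatment group". The Safety population in SAP 2.1 is everyone randomized and dosed at least once, with no calendar limit, so the same number stands under both columns.

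SAP 4.6.1 splits TEAEs, TEAEs leading to treatment discontinuation and serious TEAEs "by AE onset date (AE occurs before 01 March 2020, vs AE occurs on or after 01 March 2020". It states no denominator for this split and no adjustment for exposure.

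Elsewhere the SAP does take account of time. In 4.3.1, each subject's "study drug exposure and compliance prior to 01 March 2020 and on or after 01 March 2020 will be calculated" separately, with rules for women who finished before the date, women first dosed on or after it, and women who straddle it. In 4.6.1, TEAEs by patch type also get an exposure-adjusted rate: subjects with a TEAE over total on-treatment subject-years.

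**The concern.** A percentage of subjects with an event grows with the time over which they are observed. If the arm's follow-up is unevenly divided around 01 March 2020, the period with more follow-up shows the higher percentage, whether or not anything changed in March 2020. Putting all Safety subjects under both columns hides this, because the equal denominators suggest equal opportunity for an event. SAP 4.3.1 provides for women with no exposure at all on one side of the date.

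At stake is the reading of an exploratory assessment. A reader could take a rise or fall in procedures, new medications or TEAEs as a pandemic effect when it only reflects enrolment timing. The artefact can run in either direction, so it cannot be allowed for by eye.

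**Working it through.** The plan states no expected figure for these tables, so there is none to reproduce. Enrolment dates and event rates are not in the documents; those used below are assumptions. Every calculation assumes no pandemic effect.

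**Step 1: constant rate, one subject-year per subject.** Inputs: rate 0.2 per subject-year (assumed) and share *s* of follow-up before the date (assumed 20%, 30%, 40%). The percentage with at least one event is 1 − exp(−0.2*s*) before and 1 − exp(−0.2(1 − *s*)) after.

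| *s* | Before | After | After/before |
|---|---|---|---|
| 0.2 | 1 − exp(−0.04) = 3.9% | 1 − exp(−0.16) = 14.8% | 3.77 |
| 0.3 | 1 − exp(−0.06) = 5.8% | 1 − exp(−0.14) = 13.1% | 2.24 |
| 0.4 | 1 − exp(−0.08) = 7.7% | 1 − exp(−0.12) = 11.3% | 1.47 |

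The true rate ratio is 1.00 in each row. Every subject here has time on both sides of the date, so the distortion comes from unequal follow-up alone.

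**Step 2: explicit accrual.** Counting runs from Day 1 to 30 days after last dose (SAP 4.3.6). With 12 months of treatment and 30-day months, that is 13 months. Assume a 20% risk over the window, so the hazard is −ln(0.8)/13 = 0.0172 per month, or about 0.206 per 12 months. Assume uniform accrual between two months relative to 01 March 2020, with no dropout. Average 1 − exp(−hazard × time in period) over the arm.

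| Accrual (months) | No time before / no time after | Before vs after, all Safety | Ratio, all Safety | Ratio, only women at risk in the period |
|---|---|---|---|---|
| −12 to 0 | 0% / 0% | 9.6% vs 11.2% | 1.16 | 1.16 |
| −6 to 0 | 0% / 0% | 5.0% vs 15.7% | 3.16 | 3.16 |
| −9 to +3 | 25% / 0% | 5.5% vs 15.1% | 2.75 | 2.06 |
| −3 to +3 | 50% / 0% | 1.3% vs 19.0% | 14.97 | 7.49 |
| −18 to −6 | 0% / 42% | 17.1% vs 3.4% | 0.20 | 0.34 |

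Ratios are taken before rounding. Risks of 10% and 40% give the same pattern.

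Women wholly on one side of the date add to the problem but are not its main cause. With accrual from −6 to 0 months there are none, yet the ratio is 3.16. Restricting each denominator to women at risk therefore leaves most of the distortion.

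**Step 3: the same settings as rates.** Expected events in a period equal rate × subject-time, so events per subject-year have a ratio of 1.00 in every row. If the numerator is instead subjects with an event, as in the SAP's patch-type rate, a small residual remains. From Step 1 at *s* = 0.2: 0.0392/0.2 = 0.196 before and 0.1479/0.8 = 0.185 after, ratio 0.94, against 3.77 for the percentages. At *s* = 0.3 and 0.4 the ratios are 0.96 and 0.98.

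**The case against.** The tables are exploratory and descriptive, their denominator is openly stated for medications and procedures, and no test is attached. Counts accompany the percentages and by-subject listings are planned. Exposure before and after the date is reported under SAP 4.3.1, and disposition by randomization date under 4.1, so a careful reader can see any imbalance. SAP 4.6 leaves room for further pandemic summaries. All of this stands and keeps the consequence low. It does not make the two percentages comparable, and the reader would have to build the adjustment unaided.

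Some stronger readings are tempting, but the documents do not support them.

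- That every table split at this date is affected. Exposure and compliance cut each subject's own time, and disposition and demographics divide subjects by randomization date. Only medications and procedures state the all-Safety denominator; for TEAEs it is simply not given.
- That a woman first dosed after 01 March 2020 cannot have an item before it. Concomitant procedures are "defined as those procedures with a start date on or after the date of the first dose of study drug (Day 1") onward, but 4.3.5 and 4.3.6 also count items still ongoing at first dose, and the date split covers prior items too. SAP 4.6.1 counts as TEAEs those earlier events that worsen on treatment. For prior items an all-Safety denominator is not a structural error.
- That the existing split in 4.3.1 can serve as the denominator unchanged. It stops at last dose, while procedures, medications and TEAEs are counted for 30 days more. A woman whose last dose fell just before the date would have zero time after it but could still contribute an event there.

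**Conclusion.** The point holds for the medication and procedure summaries split at 01 March 2020, and for the TEAE split in that it defines neither a denominator nor an exposure adjustment. Without time at risk, the before and after percentages are not comparable. Under no true change, the assumed settings give 3.9% vs 14.8%, 5.8% vs 13.1% and 7.7% vs 11.3% in the simple model. In the accrual patterns tabulated, the after/before ratio runs from 0.20 to 14.97. These sizes rest on assumed rates, constant hazards and assumed enrolment dates. The actual imbalance, and its direction, cannot be read from the documents.

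A reader might infer that a difference between the columns would reflect enrolment timing and nothing else. That goes too far: a real pandemic effect could be mixed in, and the table cannot separate the two.

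The arms can still be compared roughly fairly within one period, since 1:1 randomization gives both the same expected spread of follow-up around the date. The primary analysis is unaffected. This is a cheap improvement of low consequence.

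**What to change.** For TEAEs, and for procedures and medications newly started on or after first dose, add a column with events per subject-year at risk in each period. Time at risk runs from first dose to 30 days after last dose, or to end of follow-up if earlier, and is cut at 01 March 2020. Event counts are the better numerator. Subjects with events, as in the SAP's patch-type rate, are acceptable with the small residual noted in the working.

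State the denominator for the TEAE split in 4.6.1. Footnote the medication and procedure tables to say that the all-Safety percentages are not comparable across periods. Leave prior medications and prior procedures as counts, since time at risk on study has no meaning for them.

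The cost is SAP wording, one extra column and a short derivation from dates already collected. It extends the exposure split in 4.3.1 by the 30-day window and applies to this split the kind of rate the SAP already plans by patch type. No new data are needed.
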